2.3.2 Potential Benefits

There are no known benefits to subjects participating in this trial. The knowledge gained in this trial may help society, especially those requiring treatment or prophylaxis of invasive fungal infections.

3 STUDY DESIGN, OBJECTIVES AND ENDPOINTS OR OUTCOME MEASURES

3.1 Study Design Description

This is a Phase 1, single-center, three-part, prospective, randomized, double-blind trial of single- and multiple-ascending doses of rezafungin administered by SC injection to healthy adult subjects and a two-period crossover bioavailability study with two dosing sequences of rezafungin administered by SC → IV or IV → SC doses to healthy adult subjects.

3.1.1 Dosing Scheme and Duration of Study

3.1.1.1 Part 1 (SAD)

In Part 1 of this trial, 44 subjects will be split into six cohorts – one cohort of 4 subjects (3 rezafungin, 1 placebo) and five cohorts of 8 subjects each (6 rezafungin, 2 placebo) – will be randomized to receive single SC doses of rezafungin or placebo with dose escalation separated by a minimum of 4 weeks. Single-dose levels of rezafungin to be assessed will follow an ascending single-dose regimen in all except Cohort 1. The 1, 10, 30, 60, and 100 mg doses will be administered as 0.1 – 1.0 mL SC injections (abdomen) and the 200 mg dose as 2 x 1 mL injections (in same abdominal quadrant). A schematic of the SAD study design is shown in (Table 1). Administration details are included in the protocol-specific Manual of Procedures (MOP) to this study.

Table 1: Design for SC Dosing in SAD (Study Part 1)

Cohort	Dose (mg)	Dose Volume (mL)	Number of Doses	Number of Subjects*	
				Rezafungin SC Injection	Placebo
1	1	0.1**	1	3	1
2	10	0.1	1	6	2
3	30	0.3	1	6	2
4	60	0.6	1	6	2
5	100	1	1	6	2
6	200	1 (in each of 2 injections) ***	1	6	2
Total Number of Subjects				33	11
					44

*Within each cohort two sentinel subjects will be admitted initially, and the randomization scheme will be designed to ensure that one subject will receive rezafungin and the other will receive placebo. All sentinel subject safety data through Day 30 will be reviewed by the PI prior to dosing the remainder of cohort. Safety data for each cohort through Day 30 will be confirmed by review of objective pre-defined criteria before continuing to the next cohort.

**In order to administer this dose, the drug product solution from the SC drug product vial (Rezafungin Injection, for subcutaneous use, 100 mg/mL) will be diluted 1:10 in 5% Dextrose Injection, USP. Then 0.1 mL of the diluted solution will be administered. Details are included in the MOP for this study.

***The 200 mg (2 x 1 mL) SC dose will be injected as 1 mL each in the same abdominal quadrant, separated by approximately 5 cm. Details are included in the MOP for this study.

3.1.1.2 Part 2 (MAD)

The first cohort for Part 2 of this trial (Cohort 7) can begin after the FDA has reviewed and assessed the SAD safety and PK data and providing no halting criteria have been met. In Part 2, subjects in four cohorts of 8 subjects each (6 rezafungin, 2 placebo) will be randomized to receive SC doses of rezafungin or placebo on Days 1, 8, and 15 of the MAD portion of the study. Dose levels of rezafungin to be assessed will follow an ascending multiple-dose regimen (30 mg x 3 doses, 60 mg x 3 doses, 100 mg x 3 doses, and 200 mg x 3 doses). A schematic of the MAD study design is shown in (Table 2).

Table 2: Design for SC Dosing in MAD (Study Part 2)

Cohort	Dose (mg)	Dose Volume (mL)	Number of Doses	Number of Subjects*	
				Rezafungin SC Injection	Placebo
7	30	0.3	3	6	2
8	60	0.6	3	6	2
9	100	1	3	6	2
10	200	1 (in each of 2 injections)**	3	6	2
Total Number of Subjects				24	8
				32	

*Within each cohort two sentinel subjects will be admitted initially, and the randomization scheme will be designed to ensure that one subject will receive rezafungin and the other will receive placebo. All sentinel subject safety data through Day 30 will be reviewed by the PI prior to dosing the remainder of cohort. Safety data for each cohort through Day 30 will be confirmed by review of objective pre-defined criteria before continuing to the next cohort.

**The 200 mg (2 x 1 mL) SC dose will be injected as 1 mL each in the same abdominal quadrant, separated by approximately 5 cm. Each dose will be administered in a different quadrant (total 3 quadrants). Details are included in the MOP for this study.

3.1.1.3 Part 3 (BA)

Part 3 of this study may be run in parallel with Cohort 7 of the Part 2 (MAD) portion of this study, upon completion of safety data review for all Cohorts 1-6 of Part 1 (SAD). In the unblinded Part 3 cross-over portion of this trial, 10 subjects will be randomized to one of two sequences of 5 subjects each to receive a SC→IV or IV→SC sequence of study drug administration. In sequence 1 (SC→IV), rezafungin (100 mg or MTD in Part 1) administered by SC injection on Day 1 followed by rezafungin (100 mg or MTD in Part 1) administered by IV infusion over 60 minutes on Day 22; or in Sequence 2 (IV→SC), rezafungin (100 mg or the maximum tolerated dose in Part 1) administered by IV infusion over 60 minutes on Day 1 followed by rezafungin (100 mg or the maximum tolerated dose in Part 1) administered by SC injection on Day 22. Maximum tolerated dose (MTD) is defined as the highest dose level with no withdrawals by subject or investigator due to AEs related to study product for Part 1 (SAD) Cohorts 1-6. A schematic of the BA study design is shown in [Table 3](#).

Table 3: Design for SC Dosing in Absolute BA Cohort (Study Part 3)

Sequence		Day 1 (Period 1) Dose/Volume/Route	Day 22 (Period 2) Dose/Volume/Route	Number of Subjects*
1 (SC → IV)		100 mg x 1 mL SC injection	100 mg 250 mL IV infusion	5
2 (IV → SC)		100 mg 250 mL IV infusion	100 mg 1 mL SC injection	5
Total Number of Subjects				10

*Part 3 may be run following the cohort dosed at the same dose level (100 mg or MTD) in Part 1 (SAD).

The BA of the SC dose compared to the IV dose will be determined as the ratio of the rezafungin area under the plasma concentration versus time curve (AUC) values from each administration.

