Cohorts 2-6 in the SAD and all MAD cohorts will be conducted with sentinel dosing of rezafungin (i.e., dosing in 2 subjects followed by remaining six subjects). The randomization scheme will be designed to ensure that 1 subject will receive rezafungin and the other will receive placebo in sentinel dosing. The dosing of the remaining six subjects in the same cohort will not be initiated until a minimum of 4 weeks after the second sentinel dosing, and no serious adverse events (SAEs)/adverse events (AEs) have occurred that meet the predefined objective halting criteria for sentinels. The blinded safety and clinical laboratory data from all subjects in the cohort will be reviewed and confirm that none of the dose-escalation halting rules have been met before moving to the next higher dose cohort. If any of the predefined halting criteria is met, the study enrollment and dosing will be stopped until the SMC provides recommendations regarding continuation of the study (See [Section 8.2.3](#)).

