5.2 Withdrawal from the Study, Discontinuation of Study Product, or Study Termination

5.2.1 Withdrawal from the Study or Discontinuation of the Study Product

Subjects may withdraw their consent at any time without penalty or loss of benefits to which they are otherwise entitled.

A Site PI may also withdraw a subject from the study or from receiving the study drug for any reason. Follow-Up safety evaluations will be conducted, if the subject agrees. If a subject withdraws or is withdrawn before completion of this trial, the reason(s) will be recorded in the electronic case report form (eCRF). In either case, the reason for withdrawal will be clearly documented and specifically if the reason for withdrawal was related to study drug intolerance or other adverse event.

The reason(s) for withdrawal from the study might include, but are not limited to, the following:

- Subject no longer meets eligibility criteria;
- subject meets individual halting criteria (listed in [Section 8.7.3](#));
- subject becomes noncompliant;
- medical disease or condition or new clinical finding(s) for which continued participation, in the opinion of the Site PI, might compromise the subject's safety, interfere with the subject's successful completion of this trial, or interfere with the evaluation of responses;
- subject is lost to FU;
- determined by a physician's discretion to require additional therapy not indicated in the protocol to ensure subject's health and well-being. The reason(s) for discontinuation of the study drug might include, but are not limited to;
 - subject becomes pregnant;
 - determined by a physician's discretion to require additional therapy not indicated in the protocol to ensure subject's health and well-being.

The Site PI will be explicit regarding trial FU (e.g., safety FU) that might be carried out if the subject will not receive further study drug. If the subject consents, every attempt will be made to follow all AEs through resolution. The procedures that collect safety data for the purposes of research will be included in the original ICF or the Site PI may seek subsequent informed consent using an IRB/IEC-approved ICF with the revised procedures.

The Site PI will inform the subject that data already collected will be retained and analyzed even if the subject withdraws from this trial.

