5.2.2 Handling of Withdrawals and Discontinuation of Administration

Subjects who sign and date the ICF but fail to be randomized will be defined as screen failures. Site personnel will maintain documentation for all subjects who sign an ICF.

Subjects will be informed that they have the right to discontinue study drug and/or withdraw from this trial at any time for any reason without prejudice to their medical care. If the subject has received the study drug, data collected for withdrawn subjects will be evaluated for safety and PK.

In all cases of withdrawal, the reason for withdrawal will be recorded. Subjects who receive any amount of study drug and who are discontinued from this trial will be asked to complete all FU safety assessments including FU of any AEs before termination from this trial.

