8.1.3 Adverse Events of Special Interest

In addition to SAEs, the following adverse events of special interest (AESIs) should be promptly reported to the Sponsor even if the nature of the adverse event is deemed non-serious according to the usual regulatory criteria.

Intravenous Infusion Intolerance

Events that, in the opinion of the Investigator, may represent intolerance of the IV infusion of the study drug must be recorded as AEs on the eCRF. In general, these events would be temporally associated with the IV infusion of the Sponsor’s study drug.

Phototoxicity

Due to preliminary results from a nonclinical phototoxicity study in rats, subjects should be advised to avoid sun exposure without adequate protection. Site PIs should report any AE potentially related to phototoxicity to the Sponsor.

Neuropathy and Tremors

In a rezafungin 3-month toxicity study in monkeys, there were observations of tremors, and histology consistent with axonal degeneration (potentially consistent with clinical presentation of neuropathy) first appearing at Week 6 of dosing and at 11-fold the exposure for the rezafungin for Injection dose in this study. Ataxia, axonal neuropathy, hypoesthesia, paresthesia, peripheral

motor neuropathy, peripheral neuropathy, peripheral sensory neuropathies, peripheral sensorimotor neuropathy, polyneuropathy, toxic neuropathy, and tremors should be considered AESIs. Site PIs should report any AE potentially related to neuropathy to the Sponsor.

Skin Ulcers

Skin ulcerations of any grade at study drug injection sites will be of special interest. Site PIs should report any skin ulcerations at injection sites to the Sponsor within 24 hours of site awareness. Sponsor will report skin ulcerations at injection sites to the FDA as per Expedited Reporting guidelines. Any skin ulcerations at site(s) of injection will be assessed daily while inpatient; following discharge from the unit, the Site PI will determine the frequency of monitoring until resolution or stabilization. The status of skin ulcerations will be followed until resolution.

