8.7.2 Dose Escalation Halting Rules

Sentinel Subject Halting Rules

If any of the criterion below are met, the cohort will be suspended (enrollment and dosing), and the SMC ad hoc meeting will convene:

- Any SAE (regardless of the relationship to the study drug) through 48 hours post study drug administration.
- Any Grade 2 (or higher) adverse event deemed to be related to the study medication by the PI, having an initial onset within the first 72 hours post study drug administration that does not resolve within 72 hours from onset.
- Any subject experiences skin ulceration of any grade at an injection site.

Cohort Dose Escalation Halting Rules

If any of the criterion below are met, the escalation to the next cohort will be suspended (enrollment and dosing), and the SMC ad hoc meeting will convene.

- 2 or more subjects in a cohort experience the same grade 2 (or higher) related AE (laboratory or systemic) which is coded in the same HLTG per MedDRA coding, through Day 30 (SAD) or Day 30 (MAD) of the study.

- Two or more subjects within a cohort with post-dose QTcF > 500 or change from baseline >60 ms.
- Any subject experiences skin ulceration of any grade at an injection site.

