8.7.3 Individual Halting Rules

If any of the criterion below are met, the subject will be discontinued from further dosing:

- Any SAE regardless of the relationship to the study drug, throughout the duration of the study.
- Any other condition that the Site PI judges to unduly increase the risk to the subject.
- Any subject experiences skin ulceration of any grade at an injection site. (Does not apply to infusion site).

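### The Part 3 MTD is defined only by related-AE withdrawals, so a dose that met a halting criterion can still carry the label

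*Protocol*

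**What the plan says.** **The definition.** Protocol 3.1.1.3 states: "Maximum tolerated dose (MTD) is defined as the highest dose level with no withdrawals by subject or investigator due to AEs related to study product", taken over SAD Cohorts 1 to 6. Neither document defines the term anywhere else; the SAP only lists the abbreviation. The MTD is the named alternative to 100 mg for the bioavailability part. The Protocol Summary and all four dose cells of Table 3 show 100 mg.

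**The halting rules.** The cohort rules in 8.7.2 suspend escalation and call an ad hoc SMC meeting in three situations:
- two or more subjects in a cohort have the same related Grade 2+ AE;
- "Two or more subjects within a cohort with post-dose QTcF > 500 or change from baseline >60 ms";
- one injection-site ulcer, whatever its grade.

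Section 8.7.2 also has sentinel rules, and 8.7.1 has study-wide rules that include any SAE.

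**Withdrawal.** Under 8.7.3, a subject who meets an individual rule is affected only in that "the subject will be discontinued from further dosing". Section 5.2.1 opens its list with "The reason(s) for withdrawal from the study might include, but are not limited to, the following".

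**The safeguards.** When a criterion is met, 3.1.3 says "the study enrollment and dosing will be stopped until the SMC provides recommendations regarding continuation of the study". Section 10.4.1 adds an SMC review before the BA part. Sections 3.1.3 and 10.4.2 require FDA review and agreement, and the BA dose is set after that review.

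**The concern.** A maximum tolerated dose should agree with the protocol's own account of what is not well tolerated. Here the two are separate. The halting rules use graded AEs, QTcF and ulcers. The MTD uses only the decision, by the subject or the investigator, to leave the study.

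In Part 1 that decision says little about tolerability. The only dose is given on Day 1, so no later dose can be refused. After discharge on Day 7, three scheduled contacts remain: the Day 14 visit, the Day 21 telephone call and the Day 30 visit. The protocol also has reason to keep affected subjects in view. For ulcers, 8.1.3 says "The status of skin ulcerations will be followed until resolution".

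At stake is the label handed to those who choose the Part 3 dose. The dose that triggered a halt could reach them described as tolerated. The neighbouring section shows that the link was available: 3.1.1.2 makes the start of Part 2 conditional on no halting criterion having been met, while 3.1.1.3 asks only that the Part 1 safety review be complete.

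**Working it through.** The plan gives no operating figure for the MTD, so there is none to reproduce. The check compares the rules.

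**1. Halting rules against the MTD definition**

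| Rule | Needs a withdrawal? | In the MTD definition? | Named in 8.7.3? |
|---|---|---|---|
| 8.7.2 cohort: 2+ subjects, same related Grade 2+ AE | No | No | No |
| 8.7.2 cohort: 2+ subjects, QTcF | No | No | No |
| 8.7.2 cohort: any ulcer | No | No | Yes |
| 8.7.2 sentinel: SAE within 48 hours | No | No | Yes |
| 8.7.2 sentinel: related Grade 2+ AE that does not resolve in time | No | No | No |
| 8.7.2 sentinel: any ulcer | No | No | Yes |
| 8.7.1: any SAE | No | No | Yes |
| 8.7.1: 5+ subjects, same related Grade 2+ AE | No | No | No |
| 8.7.1: any ulcer | No | No | Yes |

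All 3 of the 3 cohort criteria can be met with zero withdrawals, and 0 of the 3 enter the definition. The last column matters because 5.2.1 lists meeting 8.7.3 as a possible reason for withdrawal. Ulcers and SAEs therefore have an optional route into the MTD count. The Grade 2+ AE and QTcF criteria have none of their own; only the investigator's general judgement could bring them in.

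**2. A case where the label matters**
- Cohort 4 receives 60 mg (6 rezafungin, 2 placebo). Suppose 2 of the 6 have the same related Grade 2 AE, both stay to Day 30, and the SMC advises against escalation.
- The cohort criterion is met (2 ≥ 2). Withdrawals at 60 mg = 0, and 60 mg is the highest dose given.
- By definition the MTD is 60 mg. The planned 100 mg has not been tested in Part 1, so the MTD becomes the natural Part 3 candidate.
- If the halting criteria counted, the MTD would be 30 mg (provided 30 mg was clean), unless the SMC cleared 60 mg.

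**3. A case where it hardly matters**
- Suppose 1 of 6 at 200 mg has an ulcer and is not withdrawn. The MTD is 200 mg by definition. The planned Part 3 dose is 100 mg in any event, and an ulcer is also a listed route to withdrawal.

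**4. Illustration with assumed rates**

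Let p be the chance that a rezafungin recipient has the qualifying AE, and w the chance that an affected subject withdraws. The documents give neither. With 6 active subjects and independence:
- P(criterion met) = 1 − (1−p)^6 − 6p(1−p)^5
- P(criterion met and no withdrawal) = (1−pw)^6 − (1−p)^6 − 6p(1−w)(1−p)^5

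For p = 0.20 and w = 0.10:
- P(criterion met) = 1 − 0.262 − 0.393 = 0.345
- P(criterion met and no withdrawal) = 0.98^6 − 0.262 − 0.354 = 0.270
- Ratio = 0.270 / 0.345 = 0.78

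Over p from 0.10 to 0.50, the chance that a dose meeting the criterion still passes the MTD test is 0.71 to 0.80 for w = 0.10, 0.41 to 0.54 for w = 0.25, and 0.13 to 0.23 for w = 0.50. These figures show only that the result depends on w. They do not estimate what would have happened.

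**The case against.** The strongest reply is that the definition decides nothing by itself. The planned dose is 100 mg. The BA dose is fixed only after FDA review, and Part 3 cannot start without FDA agreement. Every met cohort criterion already goes to the SMC. Halting rules are also triggers for a pause, not limits of tolerability. They count any subject in the cohort, including the two placebo recipients in each cohort of eight, and the QTcF criterion does not require relatedness.

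Much of this stands.

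- A reader might infer that Part 3 subjects could have received a halted dose unchecked. The documents do not support that: 3.1.3, 8.2.3, 8.7.1, 10.4.1 and 10.4.2 all stand in the way.
- A reader might infer that the MTD is the default Part 3 dose. It is an alternative to 100 mg, and nothing says that it replaces 100 mg when it is higher.
- A reader might take an ulcer at 200 mg as the leading case. It is the weakest, for the reasons in the working.
- Section 5.2.2 says "Subjects who receive any amount of study drug and who are discontinued from this trial will be asked to complete all FU safety assessments". That shows an intent to keep observing, but a subject who is withdrawn and then followed up is still a withdrawal. It does not support a count of zero.
- Simply importing the 8.7.2 cohort criteria would let placebo events lower the MTD. It would also miss a dose that met only the SAE rule or a sentinel rule.

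What does not stand is the suggestion that later review repairs the definition. The reviewing bodies would still receive an MTD label that conflicts with the halting report for the same dose.

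**Conclusion.** The point holds as a minor flaw in a definition. The stated rule can give the wrong label: a dose that met a predefined halting criterion can be the MTD if nobody withdrew for a related AE. The gap is clearest for the two-subject Grade 2+ AE criterion and the QTcF criterion. The practical consequence is mainly confined to Part 1 stopping at or below 100 mg, when the MTD becomes the Part 3 candidate.

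This rests on reading 5.2.1 as permissive and 8.7.3 as stopping dosing without itself ending participation, which is what both sections say. It does not rest on the assumed rates in the illustration.

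A reader might also infer that trial results are affected. They are not. SAP section 1 reports that the study was terminated with no subject enrolled in the BA cohort, so the definition was never applied. The point matters for a restart or for a protocol that reuses the wording.

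**What to change.** Replace the definition in 3.1.1.3 with wording such as:

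> The MTD is the highest Part 1 dose level with no withdrawals for AEs related to study product, and at which no halting criterion in 8.7.1 or 8.7.2 (including the sentinel rules) was met by events in rezafungin recipients at that dose, as determined by the SMC from unblinded data, unless the SMC specifically clears that dose for Part 3.

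Restricting the count to rezafungin recipients keeps placebo events from lowering the MTD. Naming 8.7.1 and the sentinel rules covers SAEs and single-sentinel events. The five-subject rule in 8.7.1 accumulates over cohorts; restricted to one dose it adds nothing, because the two-subject rule would already have been met.

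**Cost.** One sentence and no new review step: 8.8.2 already gives the SMC unblinded data, and 10.4.1 already schedules its review before the BA part. The downside is that the MTD may come out one dose level lower (if that lower level itself qualifies). From Table 1:
- 200 to 100 mg: (200 − 100)/200 = 50%
- 100 to 60 mg: (100 − 60)/100 = 40%
- 60 to 30 mg: (60 − 30)/60 = 50%
- 30 to 10 mg: (30 − 10)/30 = 67%
- 10 to 1 mg: (10 − 1)/10 = 90%

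The SMC clearance clause lets a dose be kept where the triggering event was not a real limit.

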3.1.2 Rationale for Starting Dose

In the single-dose cynomolgus monkey trial (NC101), SC rezafungin 30 mg/kg (1 mL per injection of 100 mg/mL solution) was well tolerated with minor non-adverse skin findings ranging from very slight to slight erythema, and very slight to moderate edema. A multiple dose cynomolgus monkey trial (NC107), at doses of 30, 60, and 120 mg/kg (given as 1 mL per injection of 100 mg/mL solution in 1, 2, or 4 injections/animal every 3 days, respectively) was not tolerated, with all dose groups having adverse toxicity at the injection sites. Inflammation ranged from minimal to severe, with moderate severity and higher grades resulting in clinical and macroscopic observations of nodules, thickening, and in the most severe cases, open sores at the injection sites. At the low adverse effect level of 30 mg/kg, adverse observable skin lesions were first observed from Day 11 to 14 and were generally associated with the 4th (Day 9) injection (4-6 animals). One lesion was observed on Day 12 at the site of the 2nd (Day 3) injection, and one animal had no lesions. These findings reversed following 4 weeks of recovery at the low- and mid-dose levels and in all but one animal at the high-dose level. A suitable starting dose was selected per *Estimating the Maximum Safe Starting Dose in Initial Clinical Trials for Therapeutics in Adult Healthy Volunteers*¹⁶. This guidance recommends that if local toxicities are dose limiting the “therapeutics should be normalized to concentration (e.g., mg/area of application) or amount of drug (mg) at the application sites”.

In the NHP study, cynomolgus monkeys weighing approximately 3 kg were dosed multiple times with 30 mg/kg, or 90 mg of rezafungin.

As shown in Table 4, the SAD escalation will begin with a lower starting dose and propose an initial single-dose cohort of 1 mg/injection, which would represent roughly an hundred-fold safety margin (by total absolute dose) from the 30 mg/kg dose cohort used in both the single dose subcutaneous toxicology study (NC-101) and the lowest dose tested from the repeat dose toxicology study (NC-107).

Table 4: Proposed Starting Dose Level in the Clinic

mg	mg/kg dose	Volume	mL/kg
Cynomolgus Monkey (~3 kg)			
100	30	1 mL	0.33
200	60	2 mL*	0.67
400	120	4 mL*	1
Human (~70 kg)			
1	0.0143	0.10 mL	0.0014

*Given as multiple 1-mL injections

